### **12.3 Investigator Assessment of Adverse Events**

The investigator will assess all AEs with respect to seriousness (criteria listed above), severity (intensity or grade), and causality (relationship to study agent and relationship to research) according to the following guidelines.

#### **12.3.1 Severity**

The Investigator will grade the severity of each AE according to the CTCAE v 5.0, which can be found at [http://ctep.cancer.gov/protocolDevelopment/electronic\\_applications/ctc.htm](http://ctep.cancer.gov/protocolDevelopment/electronic_applications/ctc.htm)

#### **12.3.2 Causality**

Causality (likelihood that the event is caused by the study agent) will be assessed considering the factors listed under the following categories:

##### **Definitely Related**

- reasonable temporal relationship
- follows a known response pattern
- clear evidence to suggest a causal relationship
- there is no alternative etiology

##### **Probably Related**

- reasonable temporal relationship
- follows a suspected response pattern (based on similar agents)
- no evidence of a more likely alternative etiology

##### **Possibly Related**

- reasonable temporal relationship
- little evidence for a more likely alternative etiology

##### **Unlikely Related**

- does not have a reasonable temporal relationship  
OR
- good evidence for a more likely alternative etiology

##### **Not Related**

- does not have a temporal relationship  
OR
- definitely due to an alternative etiology

**Note:** Other factors (eg, dechallenge, rechallenge) should also be considered for each causality category when appropriate. Causality assessment is based on available information at the time of the assessment of the AE. The investigator may revise the causality assessment as additional information becomes available.

## **12.4 Investigator Reporting Responsibilities to the Sponsor**

### **12.4.1 Adverse Events**

AE data will be submitted to the IND sponsor when requested for periodic safety assessments, review of IND annual reports, review of IND safety reports, and preparation of final study reports.

### **12.4.2 Serious Adverse Events**

All SAEs (regardless of relationship and whether or not they are also UPs) must be reported on the safety expedited report form (SERF) and sent to the CSO by fax or email attachment. Deaths and immediately life-threatening SAEs must be reported to the CSO within 1 business day after the site becomes aware of the event. All other SAEs must be reported within 3 business days of site awareness.

### **12.4.3 Unanticipated Problems**

Ups that are also AEs must be reported to the CSO by fax or e-mail attachment using the NIH Problem Report Form no later than 7 calendar days of site awareness of the event. UPs that are not AEs are not reported to the CSO.

#### **12.4.4 Pregnancy**

All pregnancies will be reported on the Pregnancy Notification/Outcome Form to the CSO within 1 business day from site awareness.

Pregnancy outcome data (eg, delivery outcome, spontaneous or elective termination of the pregnancy) will be reported to the CSO within 3 business days of the site's awareness.

Although pregnancy itself is not an AE, events that meet SAE criteria during pregnancy, delivery, or in the neonate (eg, congenital anomaly/birth defect) are reportable on the SERF.

In the event of pregnancy, the following steps will be taken:

- Discontinue the study agent and procedures but continue to follow-up for safety.
- Unblind the participant.
- Study team will enroll participant in pregnancy registry.
- Report to the DSMB.
- Advise research participant to notify the obstetrician of study participation and study agent exposure.

#### **12.5 Sponsor's Reporting Responsibilities**

SUSARs, as defined in Title 21 of the United States Code of Federal Regulations (CFR) Part 312.32 and determined by the IND sponsor, will be reported to FDA and all participating investigators as IND Safety Reports.

The IND sponsor will also submit an IND Annual Report of the progress of the investigation to the FDA as defined in 21 CFR 312.33.

#### **12.6 Pausing Rules for Individual Participants**

Pausing is the suspension of administration of study agent to a single participant until a decision is made whether or not to resume administration of the study agent.

The pausing criteria for a single participant in this study include any of the following:

- A participant experiences an SAE that is unexpected and possibly, probably, or definitely related to a study agent.
- A participant experiences two grade 3 or greater AE that is unexpected and possibly, probably, or definitely related to a study agent.
- A participant develops a serious infection or an opportunistic infection, per the sarilumab package insert.
- A participant develops one of the following lab abnormalities, per the sarilumab package insert:

- ANC < 1000/ $\mu$ L.
- Platelet count < 100,000/ $\mu$ L.
- ALT or AST > 3.0  $\times$  ULN.
- Any safety issue that the site investigator determines should pause administration of a study agent to a single participant.

### **12.6.1 Reporting a Pause**

If a pausing criterion is met, then a description of the AE(s) or safety issue must be reported by the PI or designee within 1 business day to the CSO and the DSMB by fax or email, and to the IRB according to their requirements.

### **12.6.2 Resumption of a Paused Participant**

The CSO, in collaboration with the PI, will determine whether or not it is safe to resume administration of the study agent to the participant. The PI will notify the IRB of the decision on resumption of the study agent. If the pause was initiated because of lab abnormalities, then per the sarilumab package insert upon resumption, the sarilumab dose may be reduced from 200 to 150 mg after lab values return to stated thresholds. The decision to modify the dose will be made by the PI in consultation with the CSO, and reported to the DSMB. The sarilumab dose can be raised to 200 mg again as clinically appropriate, at the discretion of the PI, CSO, and/or DSMB.

### **12.6.3 Discontinuation of Study Agent for Individual Participants**

Permanent discontinuation of study drug will occur per the sarilumab package insert if:

- ANC < 500/mL.
- Platelet count < 50,000/ $\mu$ L.
- ALT > 5  $\times$  ULN

Participants who do not resume study agent during the randomized, double-blind portion of the study will continue to be followed for 16 weeks, and then be encouraged to have an early termination visit (section 6.2.6). Participants who do not resume study agent during the open-label portion will be encouraged to have an early termination visit (section 6.3.3) shortly after the decision is made not to resume.

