### 3.1 Description of the Study Design

This is a phase 2, double-blinded, randomized, placebo-controlled study to evaluate the efficacy of sarilumab as treatment for ISM. Patients with ISM will receive either 200 mg of sarilumab or placebo via SC injection Q2W for a total of 16 weeks (8 doses). Participants will return for a follow-up visit 2 weeks after the final dose (treatment peak), and then again 12 weeks later. Participants will be evaluated for clinical improvement of ISM-related symptoms, drug-related AEs, and molecular markers of ISM. After the week 28 visit, all participants will have the option to continue sarilumab for 52 more weeks, at 200 mg administered via SC injections. Participants will continue to be monitored on a regular basis for safety concerns, as instructed in the study drug's package insert.

Throughout the study, if a participant's lab results meet pausing criteria (section 12.6), then at the discretion of the PI, CSO, and data and safety monitoring board (DSMB), the dose may be temporarily reduced to 150 mg until the lab values return to normal.

A schematic of the study design is presented in [Figure 1](#).

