### Laboratory Abnormalities

Decreased neutrophil count less than 1000/ $\mu$ L occurred in patients on combination therapy and occurred in 6% and 4% of patients in the 200-mg sarilumab + DMARD and 150-mg sarilumab + DMARD groups, respectively, compared to no patients in the placebo + DMARD groups. Decrease in ANC was not associated with the occurrence of infections, including serious infections. Decreases in platelet counts less than 100,000/ $\mu$ L occurred in 1% and 0.7% of patients on 200- and 150-mg sarilumab + DMARD, respectively, compared to no patients on placebo + DMARD, without associated bleeding events. Liver enzyme elevations in the pre-rescue placebo-controlled population (sarilumab + DMARD or placebo + DMARD) are summarized in [Table 2](#).

Liver elevation was not associated with clinically relevant increases in direct bilirubin or clinical evidence of hepatitis or hepatic impairment.

Lipid abnormalities (low-density lipoproteins, high-density lipoproteins, and triglycerides) were observed at 4 weeks after initiation of therapy with no additional increases observed thereafter.

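### Section 12.6.3 sets the mandatory neutrophil stop at 500 per mL (0.5 per microlitre), so counts from 0.5 up to 500 per microlitre pause dosing but trigger no automatic permanent stop

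*Combined protocol and SAP*

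**What the plan says.** The protocol handles a laboratory abnormality in one participant in three steps.

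- **Pause (section 12.6).** Dosing is suspended if "A participant develops one of the following lab abnormalities, per the sarilumab package insert": ANC below 1000 per microlitre, "Platelet count < 100,000" per microlitre, or ALT or AST above 3 times the upper limit of normal. Section 12.6.1 requires a report to the CSO and DSMB within 1 business day.
- **Resumption (section 12.6.2).** The CSO, with the PI, "will determine whether or not it is safe to resume administration of the study agent to the participant". After a laboratory pause the dose may be lowered from 200 to 150 mg.
- **Permanent stop (section 12.6.3).** "Permanent discontinuation of study drug will occur per the sarilumab package insert if" any of three limits is met: ANC below 500 per mL, "Platelet count < 50,000" per microlitre, or ALT above 5 times the upper limit of normal.

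Section 3.1 adds that when pausing criteria are met, at the discretion of the PI, CSO and DSMB, "the dose may be temporarily reduced to 150 mg until the lab values return to normal".

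**The concern.** The neutrophil stop is the only blood-count limit in the protocol expressed per mL. Taken literally, only a reported count of essentially zero would meet it, so the rule would practically never operate.

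Neutropenia is the main laboratory risk in the protocol's own account of the drug. Section 8.1 names it as the most common reaction leading to discontinuation. Table 1 gives 10% at 200 mg against 0.2% on placebo, in rheumatoid arthritis patients who were also taking DMARDs. A mandatory stop removes discretion after severe neutropenia. With the unit as written, a participant whose count fell to, say, 100 or 400 per microlitre could be restarted if the CSO and PI agreed. The rule covers the 16-week blinded period and up to 52 weeks of open-label treatment. Most open-label doses are self-injected at home, and blood counts are scheduled 12 weeks apart after week 7 (section 6.3.1).

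**Working it through.** The limit is a stated rule and not a derived figure, so there is no calculation in the plan to reproduce. The check is a unit conversion followed by a comparison of the pause and stop limits.

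**Inputs**

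- ANC stop: 500 per mL (section 12.6.3)
- ANC pause: 1000 per microlitre (section 12.6)
- Platelet stop: 50,000 per microlitre (section 12.6.3)
- Platelet pause: 100,000 per microlitre (section 12.6)
- 1 mL = 1000 microlitres

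**1. Convert the stop.** 500 per mL ÷ 1000 = 0.5 per microlitre.

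**2. Step from pause to stop (pause limit ÷ stop limit).**

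- ANC as written: 1000 ÷ 0.5 = 2,000
- ANC at 500 per microlitre: 1000 ÷ 500 = 2
- Platelets: 100,000 ÷ 50,000 = 2

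**3. Which rule each count triggers.**

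| ANC per microlitre | Pause (below 1000) | Stop as written (below 0.5) | Stop at 500 per microlitre |
|---|---|---|---|
| 0.4 | yes | yes | yes |
| 0.5 | yes | no | yes |
| 100 | yes | no | yes |
| 250 | yes | no | yes |
| 499 | yes | no | yes |
| 500 | yes | no | no |
| 999 | yes | no | no |
| 1000 | no | no | no |

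The two versions of the stop differ for counts from 0.5 up to, but not including, 500 per microlitre. That is (500 − 0.5) ÷ 500 = 0.999, or 99.9% of the range from 0 to 500.

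**4. Units elsewhere.** Per microlitre is used for the ANC and platelet eligibility limits (section 4.2), for the risk text that begins "Decreased neutrophil count less than 1000" and the platelet figure after it (section 8.1), for both count limits in section 12.6, and for the platelet bullet directly below the ANC bullet in section 12.6.3. No other section gives an ANC level for permanent discontinuation, so nothing corrects the bullet.

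**5. Whether the resumption text fills the gap.** Section 5.4 refers to thresholds stated in section 12.6.2, but 12.6.2 lists none. Sections 3.1 and 5.4 describe the lower dose as lasting until values recover, whereas 12.6.2 describes it as starting after they recover. None of the three bars re-treatment permanently on a neutrophil count.

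**The case against.** The strongest case on the other side has five parts.

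1. **It may not be in the document.** The text was read from PDF by a program, and m and the micro sign differ by one character. This cannot be settled from the text alone. The sign did survive in the next bullet and in sections 4.2, 8.1 and 12.6, which makes a misreading less likely.
2. **If printed, it is an obvious slip.** A limit of half a cell per microlitre has no practical meaning, and the rule points to the package insert. Trained staff would very probably read 500 per microlitre. That lowers the chance of harm, but a mandatory stop should be readable from the protocol itself.
3. **Re-dosing at a low count is probably blocked anyway.** If the thresholds mentioned in section 12.6.2 are those of section 12.6, a participant at 400 per microlitre waits until the count is back to at least 1000. This is a reasonable reading. On it, what is lost is the bar on re-treatment after recovery.
4. **Other rules help.** Section 12.8 withdraws anyone who misses more than 1 dose in the randomized portion, so a pause costing two doses ends participation. Section 6.2.5 requires all eligibility criteria to be met again before open-label treatment, including ANC of at least 2000 per microlitre. Both points are correct. The first does not apply to a pause costing one dose or to the open-label year; the second is a check at entry only. Neither is a permanent stop triggered by a neutrophil count.
5. **Few participants would be affected.** The 6% with counts below 1000 per microlitre at 200 mg (section 8.1), applied to 15 active participants, gives 0.06 × 15 = 0.9 expected in the randomized period, and counts below 500 would be a subset. The 6% comes from patients also on DMARDs, which ISM patients generally do not take, so it is only a rough guide. The documents give no rate below 500.

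These points limit the consequence. They do not make the bullet right.

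**Conclusion.** The concern holds. As written, the mandatory neutrophil stop is 0.5 per microlitre, 1,000 times below the value that the rest of the protocol implies, and counts from 0.5 up to 500 per microlitre give a pause without an automatic permanent stop.

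Participants are not left unprotected. Any count below 1000 per microlitre still pauses dosing and is reported within 1 business day, the PI must obtain a DSMB recommendation (section 12.9.3), and staff may decline to resume. The loss is confined to the automatic stop. It should be fixed because it is a safety decision limit and the correction costs almost nothing. No expected number of affected participants below 500 per microlitre is claimed.

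Two assumptions remain: that per mL is what the source page prints, and that 500 per microlitre is the intended value. The second rests on the units used elsewhere and on the match with the 2 to 1 platelet step. The package insert was not available to confirm it.

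**What to change.** Check the ANC bullet in section 12.6.3 on the source page and against the cited package insert. If per mL is printed, change 500 per mL to 500 per microlitre, have the sponsor confirm the value, and notify the site. The stop then sits at half the pausing limit, as it does for platelets: counts below 500 per microlitre stop study drug permanently, and counts from 500 up to 1000 pause it.

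The cost is one unit in one bullet and a site notice. Design, sample size, power and analysis do not change.

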## **12.7 Halting Rules for the Protocol**

Halting the study requires immediate discontinuation of study agent administered for all participants and suspension of enrollment until a decision is made whether or not to continue enrollment and study agent administration.

The halting rules are:

- 2 or more participants experience the same or similar SAEs that are unexpected and possibly, probably, or definitely related to the study agent;  
*OR*
- 2 or more of the same or similar AEs in different participants that are grade 3 or above and are unexpected and possibly, probably, or definitely related to the study agent;  
*OR*
- any safety issue that the PI determines should halt the study.

The PI and/or CSO will determine if the study should be halted. In addition, the FDA may halt the study at any time following review of any safety concerns.

### **12.7.1 Reporting a Study Halt**

If a halting rule is met, then a description of the AE(s) or safety issue must be reported by the PI or designee within 1 business day to the CSO and the DSMB by fax or email, and to the IRB according to their requirements.

### **12.7.2 Resumption of a Halted Study**

The IND sponsor, in collaboration with the PI, the DSMB, and any specified safety review team will determine if it is safe to resume the study. The PI will notify the IRB of the decision on resumption of the study.

### **12.7.3 Discontinuation of Study Agent**

Participants who do not resume study agent during the randomized, double-blind portion of the study will continue to be followed for safety for 16 weeks, and then be encouraged to have an early termination visit (section 6.2.6). Participants who do not resume study agent during the open-label portion will be encouraged to have an early termination visit (section 6.3.3) shortly after the decision is made not to resume.

## **12.8 Withdrawal Criteria for an Individual Participant**

An individual participant will be withdrawn for any of the following:

- An individual participant's decision. (The investigator should attempt to determine the reason for the participant's decision.)
- Non-compliance with study procedures to the extent that it is potentially harmful to the participant or to the integrity of the study data.
- A participant misses more than 1 dose of study drug during the randomized portion of the study.

- The investigator determines that continued participation in the study would not be in the best interest of the participant.

Participants who wish to withdraw from the study will be encouraged to have an early termination visit (sections 6.2.6 or 6.3.3).

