#### 5.3 Randomization and Blinding/Unblinding Procedures

Eligible participants will be allocated 1:1 to study agent or placebo. A randomization scheme will be generated by the study statistician who will provide a randomized list of arm assignments to the NIH CC Pharmacy. A permuted block approach, with varying block sizes, will be used for the randomization process.

The participants, the investigators, and all who are involved in the evaluation of the study participants including study monitors and central laboratory personnel are blinded to a participant's treatment assignment until all participants have completed the week 16 visit. The NIH research pharmacist is identified as the unblinded third party who will be in charge of treatment assignment, maintaining study supplies/inventory list, and preparing the blinded study medication for each participant. The NIH research pharmacist will be independent of any study assessments. To maintain blinding, any discussion of the treatment assignment between the clinicians and the pharmacy staff is prohibited until the study is unblinded. Unblinding will occur when the final participant completes their week 28 visit (section 6.2.5), or in the case of early termination or study drug discontinuation, after the participant's final study visit.

Participants will be assigned a screening number after completion of the protocol consent for enrollment in the study in the Clinical Research Information Management System of the NIAID (CRIMSON). The study statistician will generate the randomization codes. These codes will be maintained by the NIH research pharmacist. A study allocation number (1, 2, etc) will be assigned when the participant is ready to be randomized. Randomization is defined as the time that the pharmacy is notified that this new participant, with this study allocation number, is being enrolled. This should coincide with the day that the first dose of study drug is administered. Randomization will continue until there are 30 participants who initiate study drug and have at least the first post-baseline QoL measurement at 4 weeks. Note that participants who do not meet these criteria still remain in the study, and attempts to obtain subsequent QoL measures should be made.

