### **15.5 Final Analysis Plan**

Several study populations are defined. The intent-to-treat (ITT) population includes all randomized participants. The modified intent-to-treat (mITT) population includes all participants who received at least one dose of sarilumab or placebo. The second modified intent-to-treat (mITT2) population further excludes the participants with no post-baseline data on the MC-QoL. The third modified intent-to-treat (mITT3) population excludes participants without 16-week MC-QoL data. The per protocol (PP) population only includes all participants with available data on 16-week MC-QoL and who report taking more than 80% of study drug.

The primary analysis will compare the groups with respect to the primary endpoint, the 16-week MC-QoL score in the mITT population using linear regression with an indicator for treatment group and the baseline MC-QoL value as a covariate. While the goal is that all participants will have a 16-week MC-QoL regardless of whether they continue drug throughout, the last observed value of MC-QoL will be carried forward to serve as the primary endpoint in the primary analysis for those participants without 16-week values. (This includes carrying the baseline value

forward, if there are no post-baseline measurements). The test will be two-sided with a 0.05 alpha level.

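### Section 12.8 withdraws anyone who misses more than one randomized dose; read as leaving the study, this works against the week-16 MC-QoL goal in 15.5 and the follow-up in 12.6.3

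*Combined protocol and SAP*

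**What the plan says.** Section 12.8 gives four grounds on which a participant is withdrawn. The third is: "A participant misses more than 1 dose of study drug during the randomized portion of the study". No object is given for the withdrawal. The fourth ground concerns continued participation in the study, and the section ends: "Participants who wish to withdraw from the study will be encouraged to have an early termination visit".

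Section 15.5 sets the aim for the primary endpoint: "While the goal is that all participants will have a 16-week MC-QoL regardless of whether they continue drug throughout". The same aim is repeated later in that section. Where the week-16 score is absent, "the last observed value of MC-QoL will be carried forward to serve as the primary endpoint in the primary analysis", and the plan adds: "This includes carrying the baseline value" forward when nothing later exists.

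Section 12.6.3 says that participants who do not resume study agent in the double-blind portion stay in follow-up for 16 weeks and are then encouraged to attend an early termination visit. Section 12.8.1 strongly encourages all randomized participants to complete follow-up and keeps them all in the analysis data set. Section 6.2.6 gives the early termination visit the same content as the week-16 visit, so it includes MC-QoL, but sets no date for it.

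**The concern.** If the missed-dose rule means leaving the study, the participants removed are those with poor adherence, and their remaining scheduled MC-QoL assessments go with them. That is missing data created by the protocol and related to treatment experience, in a trial planned around 30 people. The primary analysis then substitutes the last available score. Section 15.5 acknowledges that this assumes people who are no longer assessed are in a stable state. Someone who has just come off drug may not be.

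The bias could go either way. A good on-drug score carried forward flatters sarilumab; a score from before the drug acted does the opposite. The sensitivity analyses in 15.5 (mixed model, worst-score ranks, weighting, possible pattern mixture) examine the problem but cannot recover scores that were never collected.

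**Working it through.** **1. Which reading does the text favour?**
- For withdrawal from the study: the fourth ground and the closing sentence of 12.8 both speak of the study. Stopping agent has its own section, 12.6.3. The heading of 12.8.1 names withdrawn participants and those who stop treatment as two groups. Section 5.3 draws the same line: "or in the case of early termination or study drug discontinuation".
- For withdrawal from drug only: the verb has no object, and 12.8.1 expects follow-up to continue.

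The first reading is the more natural, but the second is open.

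**2. Do the rules overlap?** There are 8 randomized doses. A permanent stop after dose k leaves 8 - k untaken: 7 for k = 1, down to 2 for k = 6, and 1 for k = 7. If untaken doses count as missed, every stop after doses 1 to 6 meets the 12.8 criterion while 12.6.3 keeps the same person in follow-up. No section gives precedence.

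**3. How early can the carried score be?** Someone who took dose 1 meets the criterion at dose 3 (week 4) at the earliest, and MC-QoL is scheduled at that visit. Sections 5.3 and 15.2 count toward the 30 only participants who started drug and have the week-4 score. Within the 30, the carried score is therefore nominally at most 16 - 4 = 12 weeks early. Baseline is carried only for additional participants outside the 30 who have no later score. At the other extreme, if the second missed dose is dose 8 (14 × 7 ± 4 = days 94 to 102), an early termination visit from day 105 falls inside the week-16 window (16 × 7 ± 7 = days 105 to 119).

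**4. The plan's own power figure.** Rebuilding the 15.2 simulation (Beta(1.30, 2.41) × 100, correlation 0.7, baseline at least 25, declines of 60% and 10%, 15 per arm, baseline-adjusted regression) gives a difference of 22.1 points and power of 99.7%. This agrees with the stated figure of more than 90%. Simulated means are 48.7 at baseline and, at week 16, 40.0 on placebo and 17.8 on sarilumab.

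**5. Effect of one affected sarilumab participant.** Assume the true off-drug week-16 score is placebo-like (40.0).
- Full on-drug value carried: (40.0 - 17.8)/15 = 1.48 points too favourable to sarilumab.
- Baseline carried: (48.7 - 40.0)/15 = 0.58 points too conservative.

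**6. Range over assumed rates.** The documents give no rate for missing two or more doses. The 8%/3% row borrows adverse-reaction discontinuation in rheumatoid arthritis from section 8.1; the other rows are assumptions without a source in the documents. Each row assumes that no affected person has a week-16 score unless measured, and that nobody is replaced. Entries are mean difference (power).

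| Sarilumab/placebo affected | Expected sarilumab cases of 15 | Measured at week 16 | Baseline carried | On-drug value carried |
|---|---|---|---|---|
| 3%/3% | 0.45 | 21.45 (99.0%) | 21.44 (98.8%) | 22.12 (99.7%) |
| 8%/3% | 1.2 | 20.34 (96.7%) | 19.91 (95.4%) | 22.12 (99.7%) |
| 20%/10% | 3.0 | 17.70 (86.5%) | 16.82 (81.2%) | 22.12 (99.7%) |

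At 8%/3% the shift runs from 19.91 - 20.34 = -0.43 to 22.12 - 20.34 = +1.78. The two carried columns are outer bounds. Baseline cannot be carried for any of the counted 30, and the last column supposes the full benefit had been reached before dosing stopped. At 20%/10% most of the drop from 99.7% is already present in the measured column: it comes from being off drug, not from the rule.

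**The case against.** The strongest reply is section 12.8.1. Its heading expressly includes withdrawn participants, it strongly encourages all randomized participants to complete follow-up, and it keeps them in the analysis. Section 6.2.6 adds that every effort will be made to hold an early termination visit, which includes MC-QoL. Section 15.5 states a goal, not a rule, and plans for missing scores. All of this stands, and it makes the loss smaller than a bare reading of 12.8 suggests. It does not remove the problem: encouragement in 12.8.1 neither defines withdrawal nor overrides a mandatory rule, and the early termination visit has no set date.

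A reader might infer a wider contradiction, taking in 5.3, 15.2, 12.7.3 and 12.8.1. The documents do not support that. The sentence in 5.3 and 15.2 that people "still remain in the study, and attempts to obtain subsequent QoL measures should be made" covers only those who never start drug or lack a week-4 score. Section 12.7.3 concerns a study-wide halt and promises safety follow-up only. Section 12.8.1 mitigates rather than conflicts.

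A reader might also infer that the rule undermines the trial's power. The table does not show that. Section 12.8.1 also permits replacement of anyone who misses a dose, within an accrual ceiling of 60. Simulating additions until 15 per arm are unaffected, with affected people kept in the analysis, gives power (measured versus baseline carried) of 98.1% versus 97.0% at 8%/3%, and 93.4% versus 89.5% at 20%/10%. Replacement is optional, so this bounds the relief it can give.

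**Conclusion.** The point holds as a conflict between 12.8, on its more natural reading, and both the aim of 15.5 and the follow-up in 12.6.3, with no stated precedence. On the drug-only reading the conflict disappears, which is why the text should say which is meant. The textual finding rests on no assumption except that doses untaken after a permanent stop count as missed, which is needed only for the overlap with 12.6.3.

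The size is uncertain and probably small. It depends on an unknown missed-dose rate, on how many affected people attend later visits anyway, and on their off-drug course. The documents do not support a claim that the primary result is biased in a known direction, that baseline values would commonly stand in for week-16 scores, or that the power statement is wrong. It is still worth correcting before the affected visits pass, because an uncollected week-16 score cannot be obtained afterwards.

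**What to change.** Reconcile 12.8 with 12.6.3, 12.8.1 and 15.5 by separating two events: stopping study agent and leaving the study. State which one the missed-dose criterion means, and which section governs when 12.8 and 12.6.3 both apply. Then state that, whatever happens to dosing, MC-QoL is sought at the scheduled visits through week 16 from every participant who has not withdrawn consent. Count week 16 from the first dose, because 6.2.4 also ties that visit to the eighth dose, which these participants may never receive.

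All dosing, pausing and stopping rules stay with the sponsor, and no change to the primary analysis method is needed. The cost is amendment wording and a few questionnaires at visits already scheduled. The estimate will include some off-drug scores, as 15.5 already intends.
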